7.6 Stratification Factors

There are no stratification factors for this study.

7.7 Subgroups

There are no pre-planned subgroup analyses, however subgroup analyses will be done as needed.

7.8 Multicenter Clinical Trials

This is a randomized study with multiple centers.

7.9 Standard Calculations

7.9.1 Age

Age will be calculated as the number of completed years between the date of informed consent and the subject's birth date.

$$\text{Age (years)} = \text{integer of } [(\text{date of informed consent} - \text{date of birth}) / 365.25 + 0.5]$$

7.9.2 Height

For summary purposes height will be expressed in centimeters. Entries made in inches will be converted to centimeters using the formula noted below.

$$\text{Height (cm)} = \text{Height (in)} * 2.54$$

7.9.3 Weight

For summary purposes weight will be expressed in kilograms. Entries made in pounds will be converted to kilograms using the formula noted below.

$$\text{Weight (kg)} = \text{Weight (lb)} / 2.2046$$

7.9.4 Body Mass Index (BMI)

BMI will be calculated using height (in cm) and weight (in kg) according to the formula noted below.

$$\text{BMI (kg/m}^2\text{)} = \text{weight (kg)} / [\text{height (cm)} / 100]^2$$

7.9.5 Change from Baseline

For any of the effectiveness measurements change from baseline will be calculated using the formula noted below.

$$\text{Change from baseline} = \frac{\text{Post Baseline Measurement} - \text{Baseline Measurement}}{\text{Post Baseline Measurement}}$$

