#### 9.2.2 PRIMARY EFFICACY OUTCOME MEASURE

- Change in motor MDS-Unified Parkinson Disease Rating Scale (MDS-UPDRS) total score from baseline at week 12.

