7.3 Handling of Missing Data

7.3.1 Handling of Missing Data for Efficacy Evaluations

There is no imputation of missing data planned for efficacy evaluations.

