7.5 Covariates

Baseline values will be used as covariates for efficacy analysis.

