8.2.1 Primary Efficacy Outcome

The primary efficacy outcome for this study is change in motor MDS-Unified Parkinson Disease Rating Scale (MDS-UPDRS) total score from baseline at week 12.

Change in motor MDS-UPDRS total score from baseline at week 12 will be calculated for each subject using the formula in [Section 7.9.5](#). Both Treatment Group 1 and 2 will be compared with Group 3 using Analysis of Covariance (ANCOVA) with baseline value as a covariate to compare the change in motor MDS-UPDRS total score from baseline at week 12. 95% confidence interval

around the difference and P value for the treatment effect will be reported.

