8.2.2 Secondary Efficacy Outcome

The secondary efficacy outcome measures will be analyzed as follows:

8.2.2.1 Change in total MDS-UPDRS total score from baseline at week 12.

Change in total MDS-UPDRS total score from baseline at week 12 will be calculated for each subject using the formula in [Section 7.9.5](#), similar statistical methods as the primary outcome will be used for inferential statistics.

8.2.2.2 Change in MDS-UPDRS subscale scores from baseline at week 12.

Change in total MDS-UPDRS subscale scores from baseline at week 12 will be calculated for each subject using the formula in [Section 7.9.5](#), similar statistical methods as the primary outcome will be used for inferential statistics.

8.2.2.3 Change in Schwab and England (S&E) Scale total score from baseline at week 12.

Change in Schwab and England (S&E) Scale total score from baseline at week 12 will be calculated for each subject using the formula in [Section 7.9.5](#), similar statistical methods as the primary outcome will be used for inferential statistics.

8.2.2.4 Change in Parkinson's Disease Questionnaire (PDQ-39) total score from baseline at week 12.

Change in Parkinson's Disease Questionnaire (PDQ-39) total score from baseline at week 12 will be calculated for each subject using the formula in [Section 7.9.5](#), similar statistical methods as the primary outcome will be used for inferential statistics.

8.2.2.5 Change in Hoehn and Yahr (H&Y) scale total score from baseline at week 12.

Change in Hoehn and Yahr (H&Y) scale total score from baseline at week 12 will be calculated for each subject using the formula in [Section 7.9.5](#), similar statistical methods as the primary outcome will be used for inferential statistics.

8.2.2.6 Change in Clinical Global Impression-Severity (CGI-S) and Clinical Global Impression-Improvement (CGI-I) scale score from baseline at week 12.

Change in Clinical Global Impression-Severity (CGI-S) and Clinical Global Impression-Improvement (CGI-I) scale score from baseline at week 12 will be calculated for each subject using the formula in [Section 7.9.5](#), similar statistical methods as the primary outcome will be used for inferential statistics.

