9. APPENDIX 1: SCHEDULE OF ASSESSMENTS

Study Parts	Screening Part (2 weeks)	Double-Blind Treatment Part (12 weeks)				Follow-up Part Follow-up visit (4 weeks)			
		TV0 Randomization		TV1	TV2				
Treatment Visits		Day 0				FUV			
Weeks from Randomization Date (window period: \pm days)	- 2			+ 4 (\pm 3)	+ 8 (\pm 3)	+ 12 (\pm 3)			
		Pre-							
		Post-							
Written Informed Consent	X								
Inclusion/Exclusion Criteria	X								
Schedule Randomization Day	X								
Continued Eligibility		X							
Randomization		X							
Demographics	X								
Medical History	X	X							
Physical Examination	X	X		X	X	X			
Vital Signs	X	X	X	X	X	X			
Height ¹ and Weight	X	X				X			
ECG	X	X		X		X			
Serum Hematology ²	X			X	X	X			
Serum Chemistry ²	X			X	X	X			
Urine Analysis ²	X			X	X	X			
Urine Pregnancy Test ³	X	X				X			
MDS-UPDRS		X		X	X	X			
H & Y	X	X		X	X	X			
S & E		X		X	X	X			
PDQ-39		X		X	X	X			
CGI-S and CGI-I ⁴	X	X		X	X	X			
C-SSRS	X	X		X	X	X			
MMSE	X	X							
Dispense the DA-9805 or placebo ⁵			X	X	X				
DA-9805 or Placebo first dose administration			X						
Study treatment accountability				X	X	X			
Adverse Events			X	X	X	X			
Concomitant medications	X	X		X	X	X			

¹ Height only at Screening.

² Subjects who meet eligibility criteria, but have some abnormal laboratory values, based on PI review a repeat laboratory sample may be collected. The repeat laboratory reports should be reviewed by the PI to confirm eligibility prior to randomization.

³ Only for female subjects of childbearing potential.

⁴ CGI-I will be done only at Treatment Visit 1 to Treatment Visit 3

⁵ Dispense the DA-9805 or placebo at each of the clinic treatment visit, except TV3 which is the End of Treatment visit (EOT).

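### SAP 7.9.5, as read from the PDF, divides each change by the post-baseline score, so efficacy would not be analysed as the change in score the protocol names; and CGI-I has no baseline for any change formula

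*SAP*

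**What the plan says.** SAP 7.9.5 gives one definition for all efficacy measures: "For any of the effectiveness measurements change from baseline will be calculated using the formula noted below". In the text as read from the PDF the formula is a stacked fraction, with remnants of typesetting code left in: "Post Baseline Measurement} - \text{Baseline Measurement}}{\text{Post Baseline Measurement". In ordinary notation this is (Post − Baseline) / Post.

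SAP 8.2.1 uses it for the primary efficacy outcome: "Change in motor MDS-UPDRS total score from baseline at week 12 will be calculated for each subject using the formula in" Section 7.9.5. Each dose is then compared with placebo by ANCOVA with baseline as covariate, and the difference is reported with a 95% CI and P value. SAP 8.2.2.1 to 8.2.2.6 cite the same section for every secondary outcome. Protocol 9.2.2 names the primary efficacy outcome as "Change in motor MDS-Unified Parkinson Disease Rating Scale (MDS-UPDRS) total score from baseline at week 12". Neither protocol 9.2.2 and 9.2.3 nor SAP 3.1 mentions a ratio or a percentage.

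On missing efficacy data, SAP 7.3.1 says: "There is no imputation of missing data planned for efficacy evaluations".

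CGI-I is treated like the other scales. SAP 8.2.2.6 reads: "Clinical Global Impression-Improvement (CGI-I) scale score from baseline at week 12 will be calculated for each subject using the formula in" Section 7.9.5, and SAP 7.5 adds: "Baseline values will be used as covariates for efficacy analysis". Yet footnote 4 of SAP Appendix 1 states: "CGI-I will be done only at Treatment Visit 1 to Treatment Visit 3". Protocol 8.14 shows that the rating itself compares the patient with the study baseline.

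**The concern.** There are two separate defects.

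The first is the denominator. The endpoint named in both documents is a change in score, which in ordinary use is Post − Baseline. Dividing by the post score gives 1 − Baseline/Post, a unitless quantity. A programmer who follows the SAP exactly would report a treatment difference and confidence interval that cannot be read on the MDS-UPDRS scale or set beside the protocol's endpoint. Subjects with low week-12 scores would dominate the mean. A subject with a week-12 score of 0 would have no value at all, and no rule covers that case.

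The second is CGI-I. A change from baseline needs a baseline rating on the same scale, and none is collected. This holds whatever denominator is printed.

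The issue is the wrong estimand. It is not an argument about lost power, because SAP 4 states that the sample size was not derived from a power calculation. Safety analyses are not touched, since 7.9.5 covers effectiveness measurements only.

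**Working it through.** **Inputs from the documents.** Formula: SAP 7.9.5. Where it is used: SAP 8.2.1 and 8.2.2. Model: ANCOVA with baseline, two-sided 0.05 (SAP 8.2, 8.2.1). Size: 20 per arm (SAP 4). The plan states no effect size, SD or power, so there is no figure of its own to reproduce.

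**Step 1: score pairs.** Three definitions are compared: difference = P − B; SAP ratio = (P − B)/P; proportional change from baseline = (P − B)/B.

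| Baseline → post | Difference | SAP ratio | Proportional change |
|---|---|---|---|
| 20 → 10 | −10 | −10/10 = −1.00 | −0.50 |
| 20 → 30 | +10 | 10/30 = +0.33 | +0.50 |
| 10 → 5 | −5 | −5/5 = −1.00 | −0.50 |
| 30 → 25 | −5 | −5/25 = −0.20 | −0.17 |
| 5 → 1 | −4 | −4/1 = −4.00 | −0.80 |
| 4 → 0 | −4 | undefined | −1.00 |
| 0 → 0 | 0 | undefined | undefined |

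Equal moves up and down do not cancel. The same 5-point improvement counts five times as much from a baseline of 10 as from 30. Worsening can never reach +1, while improvement has no fixed floor.

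**Step 2: two arms of 20 (constructed example).**
- Arm A, all 20 subjects go from 20 to 18. Mean difference −2.0; mean ratio −2/18 = −0.11.
- Arm B, one subject goes from 20 to 2 and 19 are unchanged. Mean difference −18/20 = −0.9; mean ratio (−18/2)/20 = −9/20 = −0.45.

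The difference favours A and the ratio favours B. One subject causes the reversal.

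**Step 3: zero scores.** A post score of 0 is possible on several analysed scales. Hoehn and Yahr has a stage 0 (protocol 8.12). Every MDS-UPDRS item, including those of Part IV, has a 0 option, and the subscales are analysed under SAP 8.2.2.2. A subject who goes from 0 to 0 has a true change of 0 but no value under the ratio.

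**Step 4: illustration of power, on assumed values only.** None of these inputs is in the documents. Motor baseline mean/SD was 22/8 or 25/10 (floor 5), the effect was −5 points in one dose arm, and scores were whole points. Each scenario had 4,000 simulated three-arm trials. In the additive model, effect and noise do not depend on baseline; in the scaled model, both are proportional to it. Power at baseline 22:

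| SD of change | Additive: difference / ratio | Scaled: difference / ratio |
|---|---|---|
| 5 | 85% / 60% | 82% / 83% |
| 6 | 72% / 45% | 69% / 62% |
| 8 | 48% / 26% | 43% / 31% |

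Over both baselines the additive model loses 21 to 29 percentage points. The scaled model runs from a 3-point gain to a 12-point loss. With the effect present, 3.5 to 7.1% of motor scores were 0 under the additive model and 0 to 2.0% under the scaled one. The rejection rate of the ratio with no effect was 0.03 to 0.05.

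A second additive run used two arms, baseline 20/8 or 25/10, SD of change 5 or 7, and post scores held at 1 or more. Power was 0.55 to 0.86 for the difference and 0.22 to 0.43 for the ratio. The ratio's rejection rate with no effect was 0.022 to 0.034.

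**Step 5: CGI-I.** Both schedules of events place CGI-I at TV1 to TV3 only, and CGI-S at screening and TV0 as well. For CGI-I, B therefore does not exist: P − B and (P − B)/P cannot be computed, and there is no CGI-I baseline to enter as a covariate.

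**The case against.** The strongest objection is that the denominator may come from reading the PDF. It is the only stacked fraction in SAP 7.9; the other formulas are read inline. The heading and every endpoint description point to a plain difference. This stands as a reason to look at the page before anything else: if a plain difference is printed, the first defect disappears. Two facts count against it without settling it. The post-baseline term appears twice, which splitting a plain difference over two lines would not produce. The neighbouring weight and BMI formulas were read sensibly.

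On CGI-I, it can be said that SAP 7.5 does not require the covariate to be on the same scale, so baseline CGI-S could serve. It can also be said that the endpoint may be read as the week-12 rating, and that one component of one secondary outcome matters little in a trial whose primary objective is safety. The CGI-S suggestion is a workable choice, but the SAP does not make it, and the instruction to compute a change still cannot be carried out. The low weight is fair for CGI-I taken alone.

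It is also right that the power figures rest on invented inputs, and that even their direction depends on the model. The conclusion does not use them.

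**Conclusion.** The concern holds. As the SAP text reads, the primary and all secondary efficacy outcomes would be analysed as 1 − Baseline/Post, which is not the endpoint in protocol 9.2.2 and 9.2.3, and nothing elsewhere in the SAP overrides this. The size is shown by arithmetic: a fivefold difference in weight for the same 5-point gain, a reversed ranking of two arms through one subject, and no value at a post score of 0. This part rests on one assumption, that the fraction is printed in the SAP as it was read. If so, it must be fixed before database lock.

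The CGI-I defect does not depend on that assumption: the analysis cannot be carried out as written. No inflation of Type I error appeared in any simulated scenario, and none is claimed.

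**What to change.** 1. Check the formula in SAP 7.9.5 on the original page. If it is printed as a fraction, replace it with: Change from baseline = Post Baseline Measurement − Baseline Measurement. This then serves 8.2.1, 8.2.2.1 to 8.2.2.5 and CGI-S in 8.2.2.6.
2. Whatever the page shows, remove CGI-I from the reference to 7.9.5 in SAP 8.2.2.6. Compare the week-12 CGI-I rating of each dose with placebo by the 8.2.1 model without the baseline term (one-way ANOVA, with 95% CI and P value). If Normality is not met, use the Wilcoxon rank-sum test; protocol 9.11 allows other non-parametric methods. State in the SAP how Normality will be judged. Using baseline CGI-S as covariate would also be acceptable if it is written down in advance.
3. Add a CGI-I exception to SAP 7.5.
4. State that code 0 on CGI-S and CGI-I, which marks a rating that was not made, is treated as missing. Otherwise it would rank as the best possible score.
5. Reword the CGI-I endpoint as the week-12 score in SAP 3.1.2 and, at the next amendment, in the protocol synopsis and 9.2.3.

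The cost is a few lines of SAP text before database lock and a wording change in the protocol. No new data or visits are needed.

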8. STATISTICAL METHODS

All data collected during this study will be presented in subject data listings.

All statistical analyses will be performed using SAS® for Windows, version 9.4 or later. For

continuous variables, descriptive statistics (n, mean, standard deviation, median, minimum and maximum) will be presented by treatment group. For categorical variables both frequencies and percentages will be presented by treatment group.

8.1 Disposition and Baseline Characteristics

8.1.1 Subject Disposition and Withdrawals

There will be a detailed accounting of all subjects that signed the informed consent to participate in this trial. The following will be summarized by treatment group:

- The number of subjects who signed the informed consent
- The number of subjects who are screen failures
- The number of subjects who are randomized
- The number of subjects who received at least one study drug administration
- The number of subjects who completed the study
- The number of subjects who discontinued

Reasons for discontinuation will also be summarized.

In addition, there will also be a listing of all discontinued subjects, which will provide the clinical trial center, treatment group and the specific reason for discontinuation.

8.1.2 Major Protocol Deviations

The deviations occurring during the clinical trial will be summarized descriptively according to the following categories:

- Entrance criteria deviation
- Withdrawal criteria deviation
- Received wrong treatment or incorrect dose
- Received an excluded medication
- All other major protocol deviations

Additionally a by-subject listing of all deviations will also be prepared.

8.1.3 Demographics and Baseline Characteristics

Demographic (age, race, gender, ethnicity) and other basic baseline characteristics will be summarized and/or listed, descriptively, by treatment groups for the Safety population.

Medical history results will be provided as by-subject listings.

8.1.4 Prior and Concomitant Medications/Therapies

Prior and concomitant medications/therapies will be summarized for the Safety population.

All prior and concomitant medications recorded in the case report form will be coded to all matching Anatomic Therapeutic Classification codes using the most recent version of WHO Drug.

Descriptive summaries, by treatment group, will be prepared using the coded generic term. All prior and concomitant medications recorded in the case report form will be listed.

8.1.5 Medical History

The medical history will be summarized and/or listed descriptively.

8.1.6 Treatment Compliance

All treatment compliance data will be summarized and/or listed descriptively for the Safety population.

8.2 Analysis of Efficacy Outcome

The primary analysis of the primary and secondary outcomes will be conducted using the PP population.

To assess the consistency of the Primary Analysis results, a supportive analysis will be conducted using the ITT population. Statistical methodology for the supportive analyses will be the same as that of the primary analysis, with the exception of the analysis population.

All statistical tests for efficacy will be two-sided tests, with $\alpha=0.05$.

8.2.1 Primary Efficacy Outcome

The primary efficacy outcome for this study is change in motor MDS-Unified Parkinson Disease Rating Scale (MDS-UPDRS) total score from baseline at week 12.

Change in motor MDS-UPDRS total score from baseline at week 12 will be calculated for each subject using the formula in [Section 7.9.5](#). Both Treatment Group 1 and 2 will be compared with Group 3 using Analysis of Covariance (ANCOVA) with baseline value as a covariate to compare the change in motor MDS-UPDRS total score from baseline at week 12. 95% confidence interval

around the difference and P value for the treatment effect will be reported.

8.2.2 Secondary Efficacy Outcome

The secondary efficacy outcome measures will be analyzed as follows:

8.2.2.1 Change in total MDS-UPDRS total score from baseline at week 12.

Change in total MDS-UPDRS total score from baseline at week 12 will be calculated for each subject using the formula in [Section 7.9.5](#), similar statistical methods as the primary outcome will be used for inferential statistics.

8.2.2.2 Change in MDS-UPDRS subscale scores from baseline at week 12.

Change in total MDS-UPDRS subscale scores from baseline at week 12 will be calculated for each subject using the formula in [Section 7.9.5](#), similar statistical methods as the primary outcome will be used for inferential statistics.

8.2.2.3 Change in Schwab and England (S&E) Scale total score from baseline at week 12.

Change in Schwab and England (S&E) Scale total score from baseline at week 12 will be calculated for each subject using the formula in [Section 7.9.5](#), similar statistical methods as the primary outcome will be used for inferential statistics.

8.2.2.4 Change in Parkinson's Disease Questionnaire (PDQ-39) total score from baseline at week 12.

Change in Parkinson's Disease Questionnaire (PDQ-39) total score from baseline at week 12 will be calculated for each subject using the formula in [Section 7.9.5](#), similar statistical methods as the primary outcome will be used for inferential statistics.

8.2.2.5 Change in Hoehn and Yahr (H&Y) scale total score from baseline at week 12.

Change in Hoehn and Yahr (H&Y) scale total score from baseline at week 12 will be calculated for each subject using the formula in [Section 7.9.5](#), similar statistical methods as the primary outcome will be used for inferential statistics.

8.2.2.6 Change in Clinical Global Impression-Severity (CGI-S) and Clinical Global Impression-Improvement (CGI-I) scale score from baseline at week 12.

Change in Clinical Global Impression-Severity (CGI-S) and Clinical Global Impression-Improvement (CGI-I) scale score from baseline at week 12 will be calculated for each subject using the formula in [Section 7.9.5](#), similar statistical methods as the primary outcome will be used for inferential statistics.

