## 4.1 SCREENING AND RANDOMIZATION

### 4.1.1 SCREENING VISIT (DAY -14 TO DAY -1), UP TO 14 DAYS

The subject will sign and date the ICF, and Health Insurance Portability and Accountability Act (HIPAA) authorization (according to site practices) prior to any study-related procedures. A subject number will be assigned to each subject in successive order of consent signing at each center, beginning with 001 at each site. Each study site will receive a unique numeric designation, and will precede the subject number (e.g. at study center 01 the first two consented subjects would be 01-001 and 01-002; at study center 02 the first two consented subjects would be 02-001 and 02-002).

Screening Visit procedures are per below:

- Informed Consent will be obtained prior to any study-related procedures. (Refer to [Section 8.1](#))
- Eligibility assessment per the inclusion and exclusion criteria and diagnosis confirmation (Refer to [Section 3.1.2](#) and [Section 3.1.3](#)).
- Subject demographics (Refer to [Section 8.3](#))
- Medical history (Refer to [Section 8.4](#))
- Vital signs (Refer to [Section 8.5](#))
- Height, Weight and BMI (Refer to [Section 8.6](#))
- Physical examination (Refer to [Section 8.7](#))
- List concomitant medications (Refer to [Section 7](#))
- Laboratory assessments (hematology, biochemistry and urine analysis) (Refer to [Section 8.8](#))
- Electrocardiogram (Refer to [Section 8.9](#))
- Urine pregnancy test (Refer to [Section 8.10](#))
- Hoehn and Yahr (H&Y) Scale (Refer to [Section 8.12](#))
- Columbia-Suicide Severity Rating Scale (C-SSRS) (Refer to [Section 8.16](#))
- Clinical Global Impression-Severity (CGI-S) scale (Refer to [Section 8.14](#))
- Mini-Mental State Examination (MMSE) (Refer to [Section 8.17](#))
- Schedule randomization visit

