## 8.14 CLINICAL GLOBAL IMPRESSION

The CGI measures global severity of illness at a given point in time, and the improvement from baseline at visits following the initial baseline visit. At the screening and baseline visit, the investigator will assess the severity on a seven-point scale. At subsequent visits, the investigator will assess the subject's severity and improvement relative to baseline.

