7. DATA CONVENTION AND RELATED DEFINITIONS

7.1 Baseline Definition

For all parameters, baseline will be defined as the last available value before the randomized treatment.

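### SAP 8.2.2.6 asks for a change from baseline in CGI-I, but CGI-I is never rated before treatment, so the CGI-I tests cannot be produced as the SAP states (minor)

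*SAP*

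**What the plan says.** SAP 8.2.2.6 treats the two CGI scales together. For both, the change in "Clinical Global Impression-Improvement (CGI-I) scale score from baseline at week 12 will be calculated for each subject" by the formula in SAP 7.9.5, and inference follows methods similar to those for the primary outcome.

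- **Formula.** SAP 7.9.5 applies to every efficacy measure: "For any of the effectiveness measurements change from baseline will be calculated using the formula noted below". It contains a baseline measurement.
- **Baseline.** SAP 7.1: "For all parameters, baseline will be defined as the last available value before the randomized treatment".
- **Primary method.** SAP 8.2.1 compares each dose with placebo "using Analysis of Covariance (ANCOVA) with baseline value as a covariate". SAP 7.5 adds: "Baseline values will be used as covariates for efficacy analysis".
- **Schedule.** Footnote 4 of SAP Appendix 1, repeated in Protocol Table 4-1: "CGI-I will be done only at Treatment Visit 1 to Treatment Visit 3".
- **Visit lists.** Protocol 4.1.1 (screening) and 4.1.2 (TV0) list only the "Clinical Global Impression-Severity (CGI-S) scale". CGI-I first appears in Protocol 4.1.3, for TV1 to TV3.
- **Scale description.** Protocol 8.14: "At the screening and baseline visit, the investigator will assess the severity on a seven-point scale". Improvement relative to baseline is rated only at later visits. The CGI-I item asks the rater to compare the patient with the start of the study, and 4 means no change.

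The endpoint lists in SAP 3.1.2, Protocol 9.2.3 and the synopsis also speak of a change in CGI-I from baseline, but do not cite the 7.9.5 formula.

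**The concern.** The SAP sets a per-subject calculation for a named secondary endpoint that needs a value the study does not collect. A change score for CGI-I would also make little sense if it could be formed, because each rating already expresses change since baseline.

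At stake is the pre-specification of the CGI-I inference. If the text stands, whoever programs the analysis has to decide what the response variable is and which baseline, if any, to adjust for. If the gap is noticed only at the final analysis, that choice could be made after the treatment codes are known.

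**Working it through.** There is no plan figure to reproduce: the sample size is not power-based and no effect size is given for CGI-I. The check sets the schedule against the formula.

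**1. Ratings before the first dose, per subject**

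| Scale | Screening | TV0 | TV1 | TV2 | TV3 | Before first dose |
|---|---|---|---|---|---|---|
| CGI-S | yes | yes | yes | yes | yes | 2 |
| CGI-I | no | no | yes | yes | yes | 0 |

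The combined CGI row in both schedules is marked at screening and TV0, but footnote 4 to that row removes CGI-I there. Protocol 4.1.1, 4.1.2 and 8.14 agree.

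**2. Change score.** Under SAP 7.1 the CGI-I baseline is a value before randomized treatment. There are 0 such values, and SAP 7.3.1 plans no imputation of efficacy data. The 7.9.5 formula can be evaluated for 0 of 60 planned subjects. This follows from the schedule and does not depend on dropout.

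**3. Baseline-adjusted model.** On a simulated data set of 60 subjects (20 per arm) with CGI-I baseline missing throughout, the ANCOVA had no usable records and could not be fitted.

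**4. Could a baseline of 4 (no change) be assumed for everyone?** The documents do not provide for this. If it were done, the design matrix would hold an intercept, two dose indicators and a baseline column equal to 4 times the intercept. Its rank is 3 with 4 columns, so the baseline coefficient is not estimable. The model reduces to an unadjusted comparison of Week 12 CGI-I.

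**5. Results affected.** SAP 8.2.2.6 implies 2 scales × 2 dose-placebo comparisons × 2 populations (PP and ITT) = 8 inferential results. The CGI-I share is 1 × 2 × 2 = 4, which are undefined. The 4 for CGI-S can be computed.

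**The case against.** The best defence is that the intended analysis can be worked out. The CGI-I item is already a comparison with baseline, so the endpoint lists can be read as meaning the Week 12 rating. That reading is fair for the lists, which is why changing them is optional. It does not rescue SAP 8.2.2.6, which sends the analyst to a formula with a baseline term.

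A second defence is that the ANCOVA is brought in by reference. The SAP asks for similar methods, and SAP 7.5 does not say that the covariate must come from the same scale. This stands in part: baseline CGI-S would satisfy SAP 7.5. But the SAP does not name it, and the response variable is still missing.

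Third, a reader might infer that the plan offers no usable method for CGI-I at all. The documents do not support that. Protocol 9.11 and the synopsis allow a t-test, which needs no covariate, as well as rank-ANCOVA or other non-parametric methods, and a logit model for categorical endpoints (the synopsis adds chi-square). What is absent is an instruction to apply any of these to the Week 12 CGI-I rating in place of the change score.

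Fourth, a reader might infer that code 0 on both scales would enter the means as a score better than the best rating. Protocol 8.14 labels that code as not assessed and describes severity as having seven points, which codes 1 to 7 supply; CGI-I has the same layout. Nothing directs anyone to analyse 0 as a rating. It merits only a programming note that 0 is missing.

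**Conclusion.** The point holds, as a minor one. The CGI-I change score and CGI-I baseline covariate exist for 0 of 60 planned subjects, and four CGI-I results cannot be produced as the SAP states. This rests only on the visit schedule, the baseline definition and the formula, with the SAP's reference to the primary method read as baseline-adjusted ANCOVA.

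The reach is half of one secondary endpoint, in a trial whose sample size was chosen for descriptive results. CGI-S has its own baseline and is unaffected, as is the primary endpoint. SAP section 8 still allows raw CGI-I to be listed and summarised by treatment group, so no data are lost. No bias or loss of power is shown.

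**What to change.** Before database lock, in SAP 8.2.2.6:

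1. Limit the 7.9.5 change score to CGI-S.
2. Make the Week 12 CGI-I rating itself the response, comparing each dose with placebo, with baseline CGI-S as covariate. Use ANCOVA, or the rank-ANCOVA already allowed in Protocol 9.11 if normality is not met. Report in PP, with ITT as supportive, as for the other outcomes.
3. Add a programming note that code 0 is missing on both scales.

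Rank-ANCOVA should be named in the SAP text, because SAP 8.2.1 mentions only ANCOVA and CGI-I is a seven-category ordinal item with about 20 subjects per arm.

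The cost is two or three sentences. CGI-S at TV0 and CGI-I at TV3 are already scheduled, so no visit, rating or data field is added. Aligning the endpoint wording in SAP 3.1.2, Protocol 9.2.3 and the synopsis is optional. The protocol part needs sponsor concurrence. Protocol 13.3 exempts from prior IRB approval changes that do not involve subjects' participation, while section 14 is stricter, so the wording could wait for another amendment.
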